4.4 Treatment withdrawal criteria

- a) Patient decision to withdraw from trial and proceed to surgery
- b) Following registration, disease (that has not yet achieved a modified Mandard tumour regression grade 1 or 2; Appendix 10.2) that shows stable disease over 2 consecutive MRI scans, 4 weeks apart.

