3.0 STUDY OBJECTIVES

The primary objective of this study is to establish the time to maximum tumour response following CRT, and to investigate whether surgery can be safely avoided within the tight framework of the trial follow-up protocol in a small group of patients where the cancer becomes undetectable by imaging modalities.

It also allows the use of 18F-FDG PET/CT in combination with MRI and clinical examination (tri-modality assessment) to assess for a continued incremental response to CRT. It should be made clear that surgery is not withheld from patients entering this study. Indeed, surgery is an option at each stage of patient follow-up and is a crucial component of a patient's treatment pathway if a point is reached when there is no further regression of disease. However, should the patient refuse surgery or be medically unfit for a rectal surgery, they will continue to be followed up without surgical intervention. If a status of 'no detectable disease' by serial MRI, PET/CT and clinical assessment is achieved and the patient wishes not to have surgery, they will continue to be stringently monitored within the framework of the trial follow-up protocol.

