4.0 ELIGIBILITY

Please note that the terms "complete response", "partial response" and "stable disease" are defined by the RECIST criteria, appendix 10.1¹. The term "incremental response" is defined as a definite MRI-defined tumour volume reduction which may or may not reach the criteria for a partial response.

Patients suitable for this trial are those with locally invasive high-risk rectal adenocarcinoma with :

• No viable disease seen at MRI performed 4 weeks after long-course CRT, confirmed at 8 week MRI

Or

• Evidence of a good partial response of rectal tumour to pre-operative longcourse CRT, i.e. modified Mandard tumour regression grade (TRG) 2 on MRI, at 4 week MRI OR TRG 3 at 4 weeks and continues to show an incremental response, i.e. TRG 2, at 8 week MRI.

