2 has been achieved (if stable disease is demonstrated for such a patient on 2 consecutive scans during this period, the patient will be referred for immediate surgery). More frequent MRI scanning will be performed at the discretion of the MDM. A modified Mandard Tumour Regression Grade has been used for reporting (please see appendix 10.2).

The timing, indication and interpretation of biopsies is viewed as critically important in the context of this trial. Blind biopsies are discouraged, ie if there is no abnormality on sigmoidoscopy/ colonoscopy, then we do not recommend biopsies directed at the mucosa once occupied by the tumour. Biopsies are discouraged unless: i) an area of residual disease is visualised at (and no earlier than) 3-month Sigmoidoscopy; ii) a clinically suspicious area develops/re-appears at Sigmoidoscopy/colonoscopy; iii) MR changes raise the suspicion of recurrence.

Patients with evidence of clinical or radiological local recurrence will be referred immediately by phone and fax to the surgical team for urgent biopsy. It is anticipated that such concerns will be brought to light by MR imaging, and thus will automatically be discussed at the Unit MDM. If there is a clinical suspicion of recurrence from a source other than MR, then an urgent MRI will be considered depending on date of previous imaging. All such cases will be discussed at the next available MDM. If urgent salvage surgery is recommended, a PET/CT scan will be performed routinely pre-op to outrule occult metastatic disease.

Subjects with metastatic disease detected during follow-up will be treated according to the Unit MDM recommendation.

Patients with evidence of clinical or radiological local recurrence must be treated at least as urgently as a primary rectal cancer by the surgical team.

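### Stable disease and incremental response overlap, so a tumour that is still shrinking can meet the trigger for withdrawal and surgery while Section 3.0 treats it as still regressing

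*Protocol*

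**What the plan says.** Section 4.0 of the protocol fixes two vocabularies for change on MRI. Complete response, partial response and stable disease carry their RECIST meaning (Appendix 10.1, not shown). Incremental response is "defined as a definite MRI-defined tumour volume reduction which may or may not reach the criteria for a partial response".

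Section 4.4(b) sets a withdrawal criterion after registration. It applies to disease that has not reached modified Mandard TRG 1 or 2 and "that shows stable disease over 2 consecutive MRI scans, 4 weeks apart". Section 7.0 gives the consequence for patients not at TRG 1 or 2 at 8 weeks: "if stable disease is demonstrated for such a patient on 2 consecutive scans during this period, the patient will be referred for immediate surgery".

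Section 3.0 says when surgery becomes crucial: "if a point is reached when there is no further regression of disease". It also says that surgery remains available throughout follow-up, and that patients who refuse it or are unfit for it continue to be followed without it.

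Two other sections describe the plateau. Section 6.5 speaks of visible disease that is stable on two successive MRIs. Section 8.0 uses an unchanged (or increased) modified Mandard grade on two successive MRIs.

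Section 3.1 defines the first primary endpoint as the percentage of patients who, two years after CRT, have had no operation and are in complete response. Section 8.0 requires at least 11 of 59 for success.

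**The concern.** The withdrawal trigger uses a term whose stated meaning overlaps with the term for continuing response. The two labels lead to opposite actions: one ends deferral, the other is the reason to continue it. The trial is built to observe continued regression and to find patients who can avoid surgery, so a rule that can operate on a patient during regression works against its own objective. It also bears on primary endpoint 1, because a patient who has been operated on cannot be a success. The trigger is a conduct rule in the protocol, not an analysis detail that could be left to a later document.

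**Working it through.** **Step 1: the plan's own figure.** Inputs from Section 8.0: n = 59, success at 11 or more, rates of 10% and 25%, one-sided 0.05. With X binomial(59, p),

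P(X ≥ 11) = Σ (k = 11 to 59) C(59, k) p^k (1 − p)^(59 − k).

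- At p = 0.10: 0.031, below 0.05.
- At p = 0.25: 0.903, which agrees with the stated power of at least 90%.

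The rule is reproduced. The problem lies in who can become a success, not in this arithmetic.

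**Step 2: do the two terms overlap?** Take a definite volume reduction between two scans that does not reach a partial response.

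- It is an incremental response, because Section 4.0 expressly includes reductions short of a partial response.
- It is not a complete response, not a partial response and not growth. Of the RECIST terms named in Section 4.0, that leaves stable disease.

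This needs no numerical RECIST threshold, so it does not depend on the unseen appendix beyond the ordering of the categories.

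**Step 3: one patient through the sections.** Suppose a registered patient is at TRG 3 at 8 weeks. The next scans each show a definite reduction, less than a partial response relative to the scan before, with the grade still TRG 3.

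| Section | Reading of this patient |
|---|---|
| 4.0, incremental response | Satisfied |
| 4.0, stable disease (RECIST, scan to scan) | Also satisfied |
| 4.4(b) | Withdrawal criterion met |
| 7.0 | Immediate referral for surgery |
| 3.0 | Regression continues, so the condition that makes surgery crucial is not met |
| 6.5 | Depends on which meaning of stable is used |
| 8.0, time to maximal response | Plateau reached, because the grade is unchanged |

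The same kind of change is also treated differently before and after entry. Under 4.1(g) and 4.2(d), a further incremental response between the 4-week and 8-week scans is what makes a partial responder eligible. After registration, a change of that kind can meet the withdrawal criterion.

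**Step 4: do such patients exist under the protocol?** Section 4.0 describes suitable patients as having no viable disease or TRG 2 by 8 weeks, which would leave almost nobody for 4.4(b). But inclusion criterion 4.1(g) names no grade, Section 7.0 expressly provides for patients not at TRG 1 or 2 at 8 weeks, and 4.4(b) presupposes them. The group exists on the protocol's own text, though it is limited.

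**Step 5: effect on the endpoint.** The direction is certain: Section 8.0 takes percentages of all patients, so one operated on stays in the 59 and cannot be in the numerator. The size would require three shares: patients outside TRG 1–2 after registration, those among them shrinking by less than a partial response across consecutive scans who accept surgery, and those who would otherwise have been in complete response at two years. The protocol gives none of these.

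**The case against.** The strongest reply is that the group is small and the intent is plain. The trigger excludes TRG 1 and 2. Section 4.0 glosses incremental response in a TRG 3 patient as reaching TRG 2, which would take that patient out of the scope of 4.4(b). Sections 3.0, 6.5 and 8.0 all point to a plateau, and Section 5.9 has a single radiologist complete the MRI proformas for all trial imaging, which favours consistency. Much of this stands, and it limits the point to a subgroup. It does not remove the point: Section 4.0 gives the operative word a RECIST meaning, and a single reader still has to know which meaning to apply.

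Three stronger readings may tempt a reader, and the documents do not support them.

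- *Plateaued TRG 3 disease would never be referred.* This needs stability to be judged against the pre-CRT scan, so that an entry partial response stays a partial response. Wording about consecutive scans naturally compares one scan with the next, and the other reading would empty the clause for the patients it was written for. Section 3.0 also keeps surgery available throughout.
- *Time to maximal response is cut short.* Section 8.0 defines that endpoint by Mandard grade. A patient withdrawn after two scans at the same grade has already had the event, dated to the first of them. Only a patient whose grade is still falling outside TRG 1–2 could be affected.
- *4.4(b) and 7.0 contradict each other on scan spacing.* Section 7.0 is less specific, not contrary, and scan timing is assigned to Appendix 10.5, which is not shown.

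A loss of power could be computed for any assumed share of successes removed, but that share would be invented. Section 8.0 also allows that the true omission rate may be well above 25%.

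**Conclusion.** The point holds as a contradiction within the protocol. Read with the definitions in Section 4.0, Sections 4.4(b) and 7.0 withdraw and refer for immediate surgery a patient whose tumour is still shrinking by less than a partial response between consecutive scans. Section 3.0 makes surgery crucial only when regression has stopped.

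It concerns patients at TRG 3 or worse after registration who are willing and fit to be operated on. Its effect on the 11-of-59 endpoint has a known direction (fewer possible successes) and an unknown size. The sample size and decision rule are not in error.

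The conclusion rests on two assumptions: that Appendix 10.1 places a change that is neither response nor growth under stable disease, and that stability is judged from one scan to the next. It should be put right, but it does not undermine the design.

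**What to change.** Reconcile Sections 3.0, 4.0, 4.4(b), 6.5, 7.0 and 8.0. For the post-registration trigger, state one definition of stable that cannot be met by a scan pair that also counts as an incremental response. Name the measure (RECIST, volume or Mandard grade), the reference scan and the scan spacing, and use identical wording in 4.4(b) and 7.0. If 6.5 and 8.0 are meant to describe a different plateau from the trigger, say so. Which clinical rule applies is for the investigators to decide.

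The cost is a wording amendment, with no extra scans or patients. If the MRI data sheet in Appendix 10.4 (not shown) does not already record the category assigned to each scan pair, one added field would let the analysis show how often the trigger was met.

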5.0 TREATMENT PROTOCOL

A schema illustrating the overall treatment/ accrual plan is shown in Figure 1.

5.1 Chemo-Radiotherapy

It is anticipated that patients receiving concomitant chemotherapy will receive oral Capecitabine, though the type of concomitant chemotherapy is not stipulated by the protocol. The absence of concomitant chemotherapy, ie pre-operative RT alone, is an exclusion criterion.

Neo-adjuvant chemotherapy, as a single-agent or in combination, prior to neoadjuvant CRT, is permitted.

Prior chemotherapy for eligible patients presenting with metastatic disease is permitted.

5.2 Pelvic Radiotherapy

Long-course pelvic CRT will have been administrated in all eligible patients. It is emphasized that this protocol does not stipulate the presence or absence of a tumour boost, or planning details. Total dose, however, is stipulated.

5.3 Dose Prescription

All patients must have received a dose of at least 50Gy to the primary rectal tumour, in one or two phases.

At RMH, this is given in two phases:

- 1. Pelvis: 45 Gy in 25 fractions at 1.8Gy per fraction.
- 2. Boost: 5.4 9 Gy in 3 5 fractions at 1.8 Gy per fraction (the smaller dose will be administered if concern about the volume of small bowel included in the boost field).

5.4 18F-FDG PET/CT

18F-FDG PET/CT is incorporated as a part of this trial to assess ongoing tumour response to CRT. Three scans will usually be performed, one at 8 and 16 weeks and then 1 year after completion of CRT.

400MBq is administered for each scan, which equates to an effective dose of 8 mSv (ARSEC Notes for Guidance, 2006). There is an additional dose burden of 6mSv for the CT component of each PET/CT scan (scan range mid-skull to mid-thigh) for a standard sized 70kg adult. The total effective dose constraint per subject for these research exposures is 42 mSv.

A radiation dose of 42 mSv is roughly equivalent to 19.1 years natural background radiation. The typical risk of cancer induction in a healthy 40 year subject is 1 patient in 500 per lifetime. The latent period for radiation induced cancer is decades for solid tumours. This level of radiation is unlikely to have an untoward effect on the health of the patient.

All examinations will be completed in compliance with local IR(ME)R Employer's procedures at each site.

PET/CT scans will be assessed (visually and semiquantitatively) for significant glucose uptake and response assessment according to published guidelines and the scoring system detailed in appendix 10.3. All PET/CTs will be reviewed centrally. Where new PET findings may be due to inflammatory or infective pathology a decision on classification of disease status will be made by the PET review panel and the chief investigator/co-investigator, if biopsy of the lesion is not possible or practical. In order to ensure standardisation of PET/CT scans, central approval of QC and QA procedures should be obtained prior to recruitment at participating centres (appendix 10.3). Procedures for transfer of imaging data are also detailed in appendix 10.3.

5.5 Molecular Prognostic and Predictive Markers of Response to Treatment Substudy

5.5.1 Blood specimens for pharmacogenetic studies:

All patients will be asked to consent to an additional blood sample to be collected prior to commencement of treatment. Consent will be obtained as part of consent for study entry as blood collection is minimally invasive, although patients will be able to opt out of this part of the study if they wish. These specimens will be primarily used to correlate germ-line sequence variation with treatment outcomes, inparticular response to treatment and toxicity.

The additional blood sample will consist of two 10ml samples to be collected in EDTA-containing vacutainers (or similar blood specimen tubes), which will be mixed well, spun down and stored at minus 20°C. The samples will then be used for molecular analyses, whereas serum will be removed and stored separately.

5.5.2 Consent to obtain archived paraffin embedded specimens:

All patients will be asked for consent for part of any tissue which has already been collected and which is presently being archived to be donated for future research purposes. The tissue is likely to be specimens already collected to confirm the diagnosis of rectal adenocarcinoma and embedded in paraffin, and surplus to that which is required for diagnostic or other clinical purposes. Patients will not have to undergo any additional procedures or biopsies for this tissue to be obtained. When required, the hospital pathology departments where the specimens are archived will be contacted so that the specimens can be collected centrally and the amount required for research removed, and any surpluss returned to the hospital of origin. One way in which this tissue could be used is to make tissue arrays, however different techniques and technology may be available in the future.

Patients already enrolled in the study will be approached for retrospective consent for this part of the study.

5.5.3 Statement from the Investigators regarding tissue collection:

The Investigators are aware that there are significant and valid concerns relating to the collection of tissue from patients and its potential uses.

Any patient material (including tissue and blood) collected as part of this trial will only be used for the above programme of work which aims to correlate patient characteristics with treatment outcome. All specimens will be anonymized and patient identification by a third party will not be allowed. Results on specific analyses will not correspond with patients or third parties, since results will be of no diagnostic or therapeutic value. All patient data will be held in accordance with the Data Protection Act 1998 and the Freedom of Information Act 2000.

The collected specimens will be considered by the Investigators as a 'gift' from patients. Ownership of specimens (tissue and blood) will exclusively belong to the investigators, who will also be the custodians. Access to specimens by third parties including pharmaceutical companies or commercial researchers will not be allowed without explicit additional consent by patients.

Although patients will not be contacted for further consent, appropriate research ethics approval will be sought before any research is performed on the blood and/or tissue samples collected. This version of the protocol outlines the anticipated general areas of research to be performed on collected tissue, but a full protocol detailing all planned endpoints and analysis methods will be submitted for separate approval before research commences on any tissue or blood collected from patients in this trial.

These points will be made clear to patients at the time consent is obtained. Patients are free to decline to participate in these additional translational studies, and can withdraw consent from the study without affecting participation in the therapeutic part of the study.

5.6 Toxicity

A modified Inflammatory Bowel Disease Questionnaire and the Vaizey Incontinence Questionnaire will be used to assess bowel toxicity after Radiotherapy. These will be assessed at initial assessment then 6 monthly. Late reactions will also be scored at each clinical oncology follow-up visit using the LENT/SOMA system for relevant normal tissues.

5.7 Duration of treatment

Intensive follow-up will continue for a period of 10 years.

5.8 Pre-Registration Evaluation

- a) Complete medical history including disease related symptoms, past medical and surgical history, and co-morbidities and their treatment.
- b) Physical examination including digital rectal examination (DRE)
- c) WHO Performance Status

5.9 Consenting Process

Departmental protocol for all patients upon completion of preoperative CRT is to perform an MRI to assess response of rectal tumour to pre-operative long-course CRT at 4 weeks following completion. The following week each patient is reviewed at a Clinical Oncology clinic for toxicity review and examination, including DRE.

The trial will be discussed with eligible patients at this clinic. Each patient is then reviewed the following day at the GI Unit multi-disciplinary meeting for review of imaging and assessment of suitability for surgery. Results of 4-week MR imaging will be discussed at this time. Suitability for recruitment to the trial will be determined. Subsequent pelvic MRI will be performed 8 weeks after completion of CRT to confirm continued incremental response/sustained status of no visible disease.

Eligible patients will then be contacted, eligibility confirmed, and consent taken. Each patient will have Registration and DRE Pro Formas , and EORTC QOL, Vaizey and Modified Inflammatory Bowel Disease questionnaires completed. Baseline CT and MRI, Post-Chemoradiotherapy CT Reporting and Post-Chemoradiotherapy MRI Reporting Pro Formas will be completed by the same Radiologist, [name], for all trial imaging

This trial has been opened for multicentre participation. Trial subjects not treated at RMH are recommended to have at least one MRI within 8 weeks of completion of CRT, for comparison with MR imaging prior to neoadjuvant therapy, though this is not stipulated. All MR's will be reviewed for eligibility by [name] and discussed at the Unit MDM. Follow-up is detailed below. All imaging (MR, PET/CT and CT) will be transferred to RMH and undergo central review at RMH. Trial subjects not treated with CRT at RMH will be registered to RMH and subsequent Clinical Oncology follow-up and Imaging will take place at RMH.

5.10 Adjuvant Chemotherapy

Following registration, all patients will be discussed at a Multi-Disciplinary meeting to determine whether adjuvant chemotherapy would be of benefit. All suitable patients will then be referred to Medical Oncology clinics. The inclusion or exclusion of adjuvant chemotherapy does not form part of this protocol.

5.11 Adverse Events

Any serious adverse events will be reported to the Chief Investigator or lead investigators. The Chief Investigator has responsibility to notify CCR/LREC. All SAEs will be reported to the Chief Investigator within 24 hours and the reporting will be in accordance with the RMH/ICR SOP guidance.

5.11.1 Adverse Events not Subject to Reporting

(list of acute toxicity not necessary as trial does not recruit until after acute period, ie during and 30 days after CRT, has elapsed)

Chronic Gastro-Intestinal	LENT-SOMA grades I-III
Chronic Rectal	LENT-SOMA grades I-III
Chronic Genito-Urinary	LENT-SOMA grades I-III
Chronic Cutaneous	LENT-SOMA grades I-III
Chronic Male Sexual	LENT-SOMA all grades
Chronic Female Sexual	LENT-SOMA all grades
Chronic Vaginal	LENT-SOMA grades I-III
Chronic Vulval	LENT-SOMA grades I-III
Chronic Vascular	LENT-SOMA grades I-III
Chronic Bone	LENT-SOMA grades I-III

5.12 End of Trial Definition

The end date will be defined as the date of final follow-up appointment for the last recruited patient.

6.0 ASSESSMENT OF EFFICACY

6.1 Local Recurrence Rate / Tumour Re-growth

Local recurrence rate in patients who have achieved a sustained clinical and radiological complete response will be measured from the end date of CRT to time of documentation of local tumour recurrence/regrowth. It is emphasized that the development, or progression, of metastatic disease does not constitute local failure.

Time to Tumour regrowth / tumour recrudescence in patients who have not achieved a sustained clinical and radiological complete response will be measured from the date of start of CRT to time of documentation of tumour regrowth.

